5.2 EXCLUSION CRITERIA

Subjects will not be enrolled if they meet any of the following exclusion criteria:

1. Cervical dystonia attributable to an underlying etiology, (e.g., traumatic torticollis or tardive torticollis)
2. Predominant retrocollis or anterocollis CD
3. Significant dystonia in other body areas, or is currently being treated with BoNT for dystonia in areas other than those associated with isolated CD

[figure not shown]
4. Severe dysphagia (Grade 3 or 4 on the Dysphagia Severity Scale) at Screening or Baseline (prior to study treatment)

No additional exclusions may be applied by the investigator, in order to ensure that the study population will be representative of all eligible subjects.

Deviation from any entry criterion excludes a subject from enrollment into the study.

5.4 LIFESTYLE CONSIDERATIONS

5.4.1 THERAPIES AND MEDICATIONS

5.4.1.1 CONCOMITANT MEDICATIONS

[figure not shown]
Concomitant medications are any prescription or over-the-counter medication, including herbs, vitamins, or other nutritional supplements, used by subjects during participation in the study. Use of concomitant medications will be recorded on the Concomitant Medications electronic case report form (eCRF) from Screening through end of study.

[Redacted text block]

[figure not shown]
5.5 SCREEN FAILURES

[figure not shown]
A screen failure subject will be an individual from whom informed consent is obtained and is documented in writing (i.e., subject signs an informed consent form) but who does not meet the study eligibility requirements.

[figure not shown]

[figure not shown]
5.6 STRATEGIES FOR RECRUITMENT AND RETENTION

Sponsor will actively monitor recruitment and retention in accordance with ICH guidelines and support sites and subjects appropriately.

6.4 STUDY INTERVENTION COMPLIANCE

Due to the fact that these treatment interventions are administered IM by investigators at the study site, study intervention compliance is not applicable.

6.5 CONCOMITANT MEDICATION

Concomitant medications are any prescription or over-the-counter preparations, including herbs, vitamins, or other nutritional supplements, used by subjects during participation in the study. Use of concomitant medications will be recorded on the Concomitant Medications eCRF from Screening through end of study.

Subjects are allowed to be on a stable dose of medications (if any) used for focal dystonia treatment (e.g., anticholinergics, muscle relaxants, benzodiazepines) for at least 4 weeks prior to Baseline (Day 1) and continuing through end of study.

6.5.1 RESCUE MEDICINE

Rescue medication for CD is not allowed in this trial. Subject(s) may withdraw from the study at any time if rescue medication for CD is required.

7 STUDY INTERVENTION DISCONTINUATION AND PARTICIPANT DISCONTINUATION/WITHDRAWAL

7.1 DISCONTINUATION OF STUDY INTERVENTION

Subjects may receive one or multiple treatments of DAXI for injection. After the first treatment, subsequent treatment(s) is(are) based on the subject's response to prior treatment. A subject may not receive subsequent treatments due to significant adverse effects or lack of treatment benefit.

7.2 SUBJECT DISCONTINUATION/WITHDRAWAL FROM THE STUDY

Subjects are free to withdraw from participation in the study at any time with notification.

An investigator may discontinue or withdraw a participant from the study for the following reasons:

- Pregnancy
- Significant study intervention non-compliance (e.g., failure to follow study procedures or to keep follow-up appointments)
- If any clinical AE, laboratory abnormality, or other medical condition or situation occurs such that continued participation in the study would not be in the best interest of the subject
- The subject experiences no reduction or have an increase in the average TWSTRS-total score at Weeks 4 and 6 post-injection relative to the pre-injection TWSTRS-Total score at the beginning of the treatment cycle (i.e., **lack of efficacy**: no improvement or worsened disease status)
- If the investigator determines that another BoNT treatment is needed to control the CD symptoms and less than 12 weeks have elapsed since the last study treatment administration
- If the subject meets an exclusion criterion (either newly developed or not previously recognized) that precludes further study participation

If the subject withdraws consent and discontinues from the study, the investigator will record the reason for consent withdrawal, if one is provided by the subject, in the subject's study records and on the eCRF. If a subject withdraws consent because of an AE, that AE should be indicated as the reason for withdrawal. In the event of early discontinuation, the subject should be asked to return to the study center to complete the assessments specified in the EOS Visit.

If at any time during the study, the investigator determines that it is not in the best interest of the subject to continue, the subject will be discontinued from participation. The investigator can discontinue a subject at any time if medically necessary. Appropriate documentation in the subject's study record and eCRF

regarding the reason for discontinuation must be completed. Prior to discontinuing a subject from study participation, the investigator will discuss his/her intentions with the medical monitor or designee.

All subjects who fail to return to the study center for the required follow-up visits will be contacted by phone to determine the reason(s) why the subject failed to return for the necessary visit or elected to discontinue from the study. If a subject is unreachable by telephone after a minimum of two documented attempts (one attempt on two different days), a registered letter will be sent requesting that contact be made with the investigator.

The sponsor has the right to terminate or to stop the study at any time. Should this be necessary, both the sponsor and the investigator will ensure that proper study discontinuation procedures are completed.

Subjects who sign the informed consent form and are enrolled but do not receive the study intervention may be replaced. Subjects who sign the informed consent form, and are enrolled and receive the study intervention, and subsequently withdraw, or are withdrawn or discontinued from the study, will not be replaced.

7.3 LOST TO FOLLOW-UP

A participant will be considered lost to follow-up if he or she fails to return for scheduled visits and is unable to be contacted by the study site staff.

The following actions must be taken if a participant fails to return to the clinic for a required study visit:

- The site will attempt to contact the participant and reschedule the missed visit as soon as possible, if it does not fall within the next visit's window, and counsel the participant on the importance of maintaining the assigned visit schedule and ascertain if the participant wishes to and/or should continue in the study. If the re-scheduled visit would fall within the next visit's window, then the visit should be considered a missed visit and the subject should come in for the next scheduled visit as planned.
- Before a participant is deemed lost to follow-up, the investigator or designee will make every effort to regain contact with the participant (where possible, 2 telephone calls and, if necessary, a certified letter to the participant's last known mailing address or local equivalent methods). These contact attempts should be documented in the participant's medical record or study file.
- Should the participant continue to be unreachable, he or she will be considered to have withdrawn from the study with a primary reason of lost to follow-up.

8 STUDY ASSESSMENTS AND PROCEDURES

8.1 PROCEDURES AND METHODS

8.1.1 SUBJECT ENTRY PROCEDURES

Subject informed consent must be obtained prior to conducting screening procedures.

At screening, visit procedures include collection of samples for serum chemistry, hematology, PT, ██████████, ██████████, urinalysis, ██████████, collection of concomitant medication and medical history information. Results from clinical laboratory tests and centrally-read ECGs must be obtained and reviewed by the investigator. Any WOCBP having a positive pregnancy test pre-treatment will not be treated.

After the required screening procedures are completed and study eligibility is confirmed, as defined by the eligibility criteria in **Sections 5.1** and **5.2** a subject will be enrolled in the study and the selected dose of DAXI for injection will be prepared by a trained, dose preparer and administered by the treating investigator.

8.1.1.1 PREGNANCY

A female is considered to be of childbearing potential UNLESS she is post-menopausal (no menses for 12 consecutive months) or without a uterus and/or both ovaries.

WOCBP and male subjects must, accordingly, use an effective method of birth control such as oral contraceptive, injection, implant, patch, vaginal ring, intrauterine coil or device, tubal ligation, and female/male condom with either cap, diaphragm, or sponge with spermicide (double barrier methods). True abstinence (i.e., no heterosexual intercourse), or having a vasectomized partner is considered acceptable methods of contraception. Effective methods of contraception must be used from the start of study, Baseline visit, to 30 days after the end of study participation.

Before enrolling WOCBP in this clinical trial, investigators must review guidelines about study participation for WOCBP. The topics should generally include:

- Informed consent document
- Pregnancy prevention information
- Risks to unborn children
- Any drug interactions with hormonal contraceptives
- Contraceptives in current use
- Guidelines for the follow-up of a reported pregnancy

Prior to study enrollment, WOCBP and male subjects must be advised of the importance of avoiding pregnancy during participation in this clinical study from the Baseline visit to 30 days after the end of study participation, and the potential risk factors for an unintentional pregnancy. The subject must sign the informed consent document stating that the above-mentioned risks/consequences were discussed with her/him.

During the study, all WOCBP should be instructed to contact the investigator immediately if they suspect they might be pregnant (e.g., missed or late menstrual cycle). The investigator must immediately notify the sponsor or the authorized representative of any female subject who becomes pregnant any time during study participation. The site will be asked to follow-up with the subject periodically during the pregnancy for ongoing health and safety information through term, as applicable. Given that this is a single treatment

administration study, subjects who become pregnant after receiving their study treatment will not be automatically discontinued from the study, but will NOT receive additional study treatment for the duration of the study.

8.1.2 STUDY VISITS AND PROCEDURES

[REDACTED]

8.1.2.1 SCREENING VISIT

Subjects will be screened within 3 weeks prior to investigational product administration (Treatment Visit). Screening procedures may be performed over more than one visit within this time period, as necessary.

Specific indication medical history/prior treatment will be captured, including date of CD diagnosis and prior treatment for CD within the past year.

Subjects may be taking prohibited medications that require a washout period that extends beyond the screening period duration. These subjects are to return for a subsequent Screening Visit within 3 weeks prior to the Baseline/Treatment Visit, at which time all screening procedures should be performed as in the SOA (Table 1).

8.1.2.2 BASELINE/TREATMENT/RETREATMENT VISIT

The Baseline Treatment must be performed within 3 weeks of the Screening Visit. Subsequent to qualifying for the study, additional baseline assessments will be obtained (refer to the SOA, Table 1) ■

[REDACTED]

[REDACTED]

[REDACTED]

[REDACTED]

[REDACTED]

[REDACTED]

[REDACTED]

[REDACTED]

[REDACTED]

8.1.2.4 END-OF-STUDY VISIT

The EOS Visit for each subject in the OLS may occur when the subject:

- Prematurely withdraws from the study for specific reasons (e.g., AEs, pregnancy, or withdraws consent)
- Has no improvement or worsened disease status (i.e., lack of efficacy) after a treatment (consistent with no change or increase from baseline in the average of the TWSTRS-total score at Weeks 4 and 6 post-treatment)
- Requires another treatment less than 12 weeks from the last injection
- Reaches Week 52

Refer to the SOA (Table 1) for EOS activities.

8.1.3 VARIATION FROM SCHEDULED VISIT DAYS

To allow for scheduling flexibility, limited variation will be permitted from the specified time of each visit (Table 3).

Table 3. Allowed Variation from Scheduled Visit Days

Scheduled Visit After Each Treatment	Allowed Variation (calendar days)
Weeks 4 and 6	± 3 days
Weeks 12, 16, 20, 24, 28, 32, 36, 40, 44, 48, and 52/EOS	± 6 days
Treatment #2, #3, and #4	± 14 days

Note: Two weeks after each Treatment (at Week 2 [allowed variation: ± 3 days]), the subject will be contacted by telephone to follow up on clinical effect, any AEs or changes in concomitant medications.

A subject who experiences significant recurrence of CD symptoms (e.g. pain) during the study before his/her TWSTRS-total score reaches the target TWSTRS score may request another treatment before the next scheduled visit. In this case, the subject may have an unscheduled visit for the investigator to assess whether another treatment is warranted based on the subject's symptoms and neurologic exam findings. If the investigator confirms that retreatment is clinically indicated, the subject may receive another treatment at this visit, unless less than 12 weeks have passed since the last injection or the injection will occur after Week 40 (i.e., there is less than 12 weeks of follow up left in the 52-week study period).

Note: After each Treatment, study visits are reset to begin from that Treatment to Week 4, Week 6, Week 12, and every 4 weeks thereafter.

8.2 SAFETY AND OTHER ASSESSMENTS

Unscheduled safety assessments may be performed at any time during the study to assess any perceived safety concerns.

8.2.1 PHYSICAL EXAMINATION

A complete physical examination will include examination of the following parameters and body systems: skin, neck (including thyroid), head, eyes, ears, nose, throat, heart, lungs, abdomen, back, lymph nodes, extremities, vascular and neurological (see **Section 8.2.2** for details). If indicated based on medical history and/or symptoms, rectal, external genitalia, breast, and/or pelvic exams may be performed.

At Screening and Baseline Treatment visits, a complete physical examination will be performed. At visits post-treatment, the physical examination may be abbreviated, as deemed medically appropriate at the discretion of the investigator.

Significant physical examination findings which meet the definition of an AE will be recorded on the AE page post-treatment; significant findings that are present prior to investigational product administration are included on the Medical History page.

8.2.2 NEUROLOGICAL EXAMINATION

A standard neurological examination will include assessment of mental status, cranial nerves, motor and sensory function, reflexes, muscle strength, coordination, station and gait.

Significant neurological examination findings which meet the definition of an AE will be recorded on the AE page post-treatment; significant findings that are present prior to investigational product administration are included on the Medical History page.

8.2.3 VITAL SIGNS

Vital signs captured include height (screening only), weight, body temperature, respiration rate, sitting radial pulse rate, and sitting systolic and diastolic blood pressures.

8.2.4 PULMONARY FUNCTION TEST

Pulmonary function will be recorded using spirometry as requested by Regulatory Authorities. Parameters that will be measured are forced vital capacity (FVC), which is the total volume of air exhaled during the forced expiratory volume test, and the forced expiratory volume in the first second of exhalation (FEV₁).

8.2.5 12-LEAD ECG

A single standard supine 12-lead ECG will be obtained after a subject has rested quietly for at least 10 minutes, using equipment provided from the central reader. The ECG is to be repeated up to 2 times if the result is abnormal, as clinically appropriate. ECG data will be submitted to a central reader for measurement.

8.2.6 PREGNANCY TESTING

All WOCBP will have a serum pregnancy test at screening and urine pregnancy test at all designated post-screening timepoints as indicated in the SOA (Table 1). If the urine pregnancy test is positive, a serum pregnancy test will be performed to confirm. If any result is positive prior to investigational product administration, the subject will not be allowed to participate. Refer to **Section 8.1.1.1** for further information.

8.2.7 CLINICAL LABORATORY DATA

As outlined in Table 4, non-fasting samples for serum chemistry, hematology, PT, serum antibodies and urinalysis will be collected at designated study timepoints (refer to Table 1). Blood and urine specimens will be collected using applicable safety precautions and processed according to clinical laboratory instructions.

Table 4. Clinical Laboratory Tests

Hematology	Serum Chemistry	Urinalysis	Additional Tests

 • Hemoglobin • Hematocrit • Leukocyte count (total) • Leukocyte count (differential) • Red blood cell count • Platelet count 	
 • Glucose • Total bilirubin • Alanine aminotransferase • Aspartate aminotransferase • Alkaline phosphatase • Blood urea nitrogen • Pregnancy (WOCBP at Screening) • Potassium • Sodium • Calcium • Carbon Dioxide (Bicarbonate) • Chloride • Creatinine • Total Protein 	
 • Specific gravity • pH • Glucose • Protein • Blood • Bilirubin • Ketones 	
 • Prothrombin time (PT) • Urine Pregnancy (WOCBP only)* • Serum pregnancy test at end of study if urine pregnancy test is positive

* If positive at post-treatment timepoints, confirm by serum pregnancy test

It is the investigator’s responsibility to review the results of all laboratory tests as they become available. For each laboratory test result outside the reference range, the investigator must ascertain if the abnormal lab result is a clinically significant result for that individual subject. Likewise, if laboratory tests are taken at follow-up visits, the investigator must ascertain if this is an abnormal and clinically significant change pretreatment for that individual subject. The investigator may repeat the laboratory test or request additional tests to verify the results of the original laboratory test. The investigator must sign and date all written laboratory results (chemistry, hematology plus PT, and urinalysis) and note Not Clinically Significant (NCS) or Clinically Significant (CS) for each out of range laboratory value. If a laboratory value is determined to be a clinically significant result for that subject, this may be considered an AE. Refer to **Section 8.2** for further information.

[REDACTED]

8.2.8 INJECTION SITE EVALUATION

Injection sites will be evaluated to determine if there are any injection site reactions to the investigational product. Any injection-related pain, redness, bruising or swelling, etc., will be reported as AEs.

8.2.9 COLUMBIA-SUICIDE SEVERITY RATING SCALE

The C-SSRS is a questionnaire that prospectively assesses Suicidal Ideation and Suicidal Behavior using a semi-structured interview to probe subject responses (Appendix H). The C-SSRS is to be administered at each visit, including unscheduled ones. Both the Lifetime/Recent and Since Last Visit versions will be utilized. All assessors will receive formal training in the use of this tool.

A subject who endorses “suicidal ideation” must be referred to a mental health professional for further assessment and/or treatment.

8.2.10 DYSPHAGIA SEVERITY SCORE

The investigator will assess subjects for the presence of dysphagia at Screening, and if present, determine the severity of dysphagia. Subjects who have severe or very severe (Grade 3 or 4) dysphagia at Screening are not eligible to enroll in this study.

Investigator will re-assess the presence of dysphagia and the severity, if present, at the Baseline Treatment Visit prior to study drug administration. If severe or very severe (Grade 3 or 4) dysphagia is present at Baseline, the subject is not eligible to enroll in the study.

When subjects report dysphagia at any post-baseline visits, the investigator will determine the status (ongoing or new) and severity of dysphagia (Grade 1, 2, 3, or 4) using the dysphagia severity scale provided in Appendix I. Any post-baseline dysphagia determined by the investigator to be new or ongoing with an increase in severity (grade) relative to Baseline, will be considered an AE and will be recorded on the eCRF. When dysphagia is an adverse event, the dysphagia severity assessment should be performed at every subsequent study visits until the dysphagia has resolved or return to the pre-treatment status.

8.2.11 ADVERSE EVENTS

Adverse Events (AEs) will be graded as mild, moderate, or severe as defined in **Section 8.3.3.1** of this protocol.

8.3 ADVERSE EVENTS AND SERIOUS ADVERSE EVENTS

8.3.1 DEFINITION OF ADVERSE EVENTS (AE)

For this protocol, an **AE** is any untoward medical occurrence (e.g., sign, symptom, disease, syndrome, intercurrent illness, clinically significant abnormal laboratory finding, injury, or accident) that emerges or worsens following administration of the study drug and until the end of study participation. The untoward medical occurrence may not necessarily have a causal relationship to the administration of the investigational product. An AE can therefore be any unfavorable and/or unintended sign (including a clinically significant abnormal laboratory result), symptom, or disease temporally associated with the use of a medicinal (investigational) product, whether or not related to the medicinal (investigational) product. A TEAE is one that occurs after any exposure to treatment.

A pre-existing condition is one that is present prior to the start of the study and is to be reported as part of the subject's medical history. It should be reported as an AE only if the frequency, intensity, or the character of the condition worsens during the study.

Any clinically significant change in the study safety evaluations, (e.g., vital signs, physical/neurological examinations, etc.) post-injection must be reported as an AE.

For each laboratory test result outside the reference range, the investigator must ascertain if the abnormal lab result is a clinically significant result for that individual subject. This determination, however, does not necessarily need to be made the first time an abnormal value is observed; the investigator may repeat the laboratory test or request additional tests to verify the results of the original laboratory test. If a laboratory value is determined to be a clinically significant result for a subject, this may be considered an AE.

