9.3 PRIMARY STUDY OBJECTIVES AND ENDPOINTS

Primary Objectives:

- To evaluate the long-term safety of multiple continuous treatments of DAXI for injection
- To assess immunogenicity to BoNTA and RTP004 after multiple treatments of DAXI for injection

Primary Endpoints:

[figure not shown]
- Dose- and cycle-specific incidence of drug-related adverse events
- Dose- and cycle-specific incidence of drug discontinuation due to drug-related AEs
- Dose- and cycle-specific incidence of immunogenicity

[REDACTED]

[REDACTED]

- [REDACTED]
- [REDACTED]
- [REDACTED]

[REDACTED]

- [REDACTED]
- [REDACTED]
- [REDACTED]
- [REDACTED]
- [REDACTED]
- [REDACTED]

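### Protocol 8.3.1 and 8.2.7 make AE reporting optional for laboratory results already judged clinically significant, against the protocol's own AE definition; the effect on the drug-related AE endpoint is probably small

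*Protocol*

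**What the plan says.** Protocol 8.3.1 opens with the AE definition. Its list of untoward occurrences includes a "clinically significant abnormal laboratory finding, injury, or accident) that emerges or worsens following administration of the study drug", and the same paragraph returns to the example: "including a clinically significant abnormal laboratory result". The third paragraph sets a general rule: "Any clinically significant change in the study safety evaluations, (e.g., vital signs, physical/neurological examinations, etc.) post-injection must be reported as an AE". Laboratory tests are named among the safety evaluations in the Synopsis (1.1) and among the safety assessments in 4.3.

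The fourth paragraph of 8.3.1 asks the investigator to judge the clinical significance of each out-of-range result, allows repeat testing first, and ends: "If a laboratory value is determined to be a clinically significant result for a subject, this may be considered an AE". Section 8.2.7 requires a written mark of clinically significant (CS) or not (NCS) for each out-of-range value, and then says: "If a laboratory value is determined to be a clinically significant result for that subject, this may be considered an AE".

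The first primary endpoint in Protocol 9.3 is the "Dose- and cycle-specific incidence of drug-related adverse events"; SAP 4.1 has the same endpoint. SAP 9.3 treats an AE as related if its relationship is definite, probable or possible. SAP 9.5 lists out-of-range and CS results with the investigator's determination, and gives summary statistics and shift tables by dose and cycle.

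**The concern.** Investigator judgment properly enters when a value is marked CS or NCS. The *may* sentence applies after that step and adds a second choice with no visible criterion. A new CS result is an AE under the definition, compulsory to report under the general rule, and optional under the last sentence.

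At stake is consistent capture of one component of a primary endpoint. Relationship to study drug is assessed for AEs (Protocol 8.3.3.2). A CS result that is never entered as an AE therefore gets no relationship rating and cannot count as drug-related, whatever the investigator would have thought of its cause. The trial is open-label, with descriptive summaries and no concurrent arm without DAXI, so no between-group contrast would offset under-reporting.

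**Working it through.** No figure in the plan depends on this wording, so there is nothing to reproduce. The check is a comparison of texts.

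**Step 1. The rules side by side**

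| Place | Finding covered | Rule |
|---|---|---|
| 8.3.1, paragraph 1 | CS laboratory finding, emerging or worsening after study drug | is an AE by definition |
| 8.3.1, paragraph 3 | CS change in safety evaluations | "post-injection must be reported as an AE" |
| 8.3.1, paragraph 4 | CS laboratory value, no timing stated | *may* be an AE |
| 8.2.7 | CS laboratory value, no timing stated | *may* be an AE |
| 8.2.8 | injection-related reactions | are to be reported as AEs |
| 8.2.10 | new or worsened dysphagia | counts as an AE and is recorded |

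Laboratory findings are the only ones here given an optional rule after the investigator has decided that they matter. The wording occurs twice, so it is not an isolated slip. Section 8.2.7 then refers the reader to Section 8.2 rather than 8.3.1; the visible text directly under the 8.2 heading concerns unscheduled assessments and gives no AE criterion.

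**Step 2. What happens to a CS result not entered as an AE**

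- AE elicitation (8.3.5) relies on asking how the subject has felt since the last visit, which will not bring out an asymptomatic laboratory finding.
- The SAP 9.5 listing keeps the result and its CS flag. The shift tables show its low, normal or high category (normal or abnormal for urinalysis) at the weeks they cover.
- SAP 9.3 counts an AE with missing relationship as definite, but that protects only events already recorded as AEs.
- No visible step in either document checks CS flags against AE records.

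The finding is therefore kept and the causality rating is lost.

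**Step 3. Scale, by assumption only**

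Let q be the share of subjects with a treatment-emergent CS result that would be judged drug-related and who have no other drug-related AE in the same dose and cycle. Let s be the share of these results that sites report. Incidence is then understated by q × (1 − s). The documents give neither input. Assume q = 0.5% to 3%, and use 350 as a round number of subjects:

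- s = 0 (none reported): 0.5 to 3 percentage points; 0.005 × 350 = 1.75 to 0.03 × 350 = 10.5 subjects.
- s = 50%: 0.25 to 1.5 points; 0.875 to 5.25 subjects.

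These figures show how the loss scales. They are not estimates.

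**The case against.** The strongest reply is that the passages can be read together. The paragraph ending in *may* concerns every out-of-range result, with no time limit, and screening results are reviewed too (8.1.1). A CS result present before dosing and not worsened is not an AE, so some CS results are AEs and some are not, and *may* would fit that. On this reading, a CS change after injection falls under the definition and the compulsory rule, which already give the right outcome. This is possible, and the last sentence grants no express exemption. But the protocol does not say it, pre-existing conditions have their own paragraph in 8.3.1, and in 8.2.7 the *may* sentence comes after the discussion of follow-up tests. A site could reasonably take it at face value.

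A reader might also infer that unreported results are lost to the analysis for good. The documents do not support that. The CS mark is required in writing, the SAP lists it, and 8.3.4.1 has CS abnormalities at the end of study notified to the medical monitor and followed. Such a result can be found and queried.

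It is also fair that redacted text in 8.2.7 and the SAP could hold a further rule. None is visible.

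**Conclusion.** The inconsistency is in the current text and should be reconciled. Its consequence is limited: a new CS laboratory result may reach the laboratory outputs without the causality rating that the drug-related AE endpoint needs.

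The size cannot be estimated from the documents and is probably small. Only a result judged drug-related, in a subject with no other drug-related AE in that dose and cycle, changes the incidence. The immunogenicity endpoint is not affected.

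Two stronger conclusions are tempting. One is a stated bias in the primary endpoint. Assuming that 2% to 5% of subjects have a new CS result and half are reported gives 0.02 × 0.5 = 1.0% to 0.05 × 0.5 = 2.5%, but both inputs are assumed and the result concerns all AEs, not drug-related ones. The other is that incidence will in fact be lowered and will differ by site. The wording permits this; nothing in the documents shows that it will happen. Leaving clinical significance and causality to the investigator is normal and is not the defect.

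**What to change.** In Protocol 8.3.1 (last sentence) and the matching sentence in 8.2.7, replace the optional wording with a rule that follows the protocol's own definition:

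- A clinically significant laboratory result that emerges or worsens after the first dose of study drug must be reported as an AE, unless it is part of an AE already reported.
- An abnormality present before the first dose and not worsened stays in medical history.

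The reference should be the first dose because SAP 6.2 (baseline) and SAP 9.3 (treatment emergence) use it. Comparing with the last value before each injection would move the reference every cycle. A result that emerged in cycle 1 and persisted into cycle 2 could then be misfiled as pre-existing.

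In 8.2.7, point the cross-reference to 8.3.1. Before database lock, query every result marked CS after the first dose against the AE data, so that a missing AE record and its relationship rating can be obtained from the site.

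The cost is two sentences of protocol text, a site reminder, one data-management check, and a few more reported AEs.
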